### **3.6.3.7 Concomitant Medications**

The collection of information on concomitant medications used by subjects following vaccination will coincide with the collection period of adverse events. The collection period for concomitant medications will be through 14 days following the last vaccination. The collection period for concomitant medications associated with the treatment of serious adverse events (SAE) will be Study Days 0-112

Concomitant medication includes prescription and non-prescription drugs or other treatments, and any monoclonal or polyclonal antibodies other than the study antibodies. The name of the medication, treatment start and stop dates (or 'ongoing'), route of administration, and indication must be recorded on the concomitant medications case report form (CRF). The indication recorded on the concomitant medications CRF must correspond to a medical term/diagnosis recorded on the adverse event (AE) CRF, or to a pre-existing condition noted in the subject's medical history, or be noted as prophylaxis, e.g., dietary supplement.

### **3.6.4 Window Periods for Clinical Laboratory, ECG, Immunology and Pharmacodynamic Blood Specimens**

There is no window for clinical laboratory tests earlier than Study Day 7. After Study Day 7 the window is approximately 10% of the Study Day number. For example At Study Day 7 the window is 0.7 days that rounds to 1 day. At Study Day 14 the window is 1.4 days that rounds to 1 day. At Study Day 42 the window is 4.2 days that rounds to 4 days.

### **3.6.5 Subject Follow-up and Contact**

All subjects who are assigned a subject identification number and receive study drug will be followed according to the protocol unless consent is withdrawn. Subjects will be instructed to contact a study team member to report new diagnoses or new or worsening adverse events and to come to the study clinic if medical attention is needed, provided the urgency of the situation permits. For emergencies and other unscheduled visits to a medical facility other than the study clinic, medical records will, to the extent possible, be obtained by the investigator.

During each clinic visit, the subject will be reminded to notify a study team member of the following:

- The occurrence of AEs and SAEs during the respective reporting periods
- Receipt of any concomitant medications during the applicable reporting period
- Plans to move or if contact information changes
- If subject has decided to withdraw from the study
- Change in general health status
- Any other change in status that may affect the subject's participation (e.g., plan to participate in another investigational study)

All deviations from protocol procedures, evaluations, and/or visits must be categorized and documented as they occur. Each deviation must be documented on a Protocol Deviation Form. When possible, missed visits and procedures must be rescheduled and performed at the nearest possible time point to the original schedule.

### **3.6.6 Loss to Follow-up**

If the site's study team members are unable to establish contact with a subject who misses a scheduled study visit, the clinical site must make every possible effort to re-establish contact and document such efforts. If contact is re-established, then the subject will resume participation in the study. If contact with the subject cannot be re-established by the subject's calculated Study Day 112 visit date, then a determination of "lost to follow-up" can be made.

### **3.6.7 Replacement of Subjects**

Subjects who fail to complete the study through Study Day 28 may be replaced at the discretion of the sponsor.

## **4 STUDY MEDICINAL PRODUCTS**

### **4.1 SYN023**

SYN023 will be supplied by Synermore Biologics.

#### **4.1.1 Receipt and Storage**

Upon receipt of study drug supplies, the study drug manager must immediately inspect all vials for damage. SYN023 will be shipped with a continuous temperature-monitoring device. Any damage or discrepancies from the packing list must be documented and promptly discussed with the sponsor and the study monitor to determine the appropriate action. SYN023 must be stored upright at 2- 8° C in a secured location with no access for unauthorized personnel. Refer to the most recent version of the Project Specific Procedures or detailed instructions regarding study drug storage.

### **4.1.2 SYN023 Preparation**

After cleaning of the vial top with an alcohol swab, the proper dose of SYN023 is withdrawn slowly from the vial with a 21 gauge needle. After cleaning of the vial top with an alcohol swab, the proper dose of SYN023 is withdrawn slowly from the vial with a 21 gauge needle avoiding foaming. Study drug should be inspected for particulate matter and discarded if present. If more than one vial of SYN023 is required the dose may be accumulated from a second vial. SYN023 must be allowed to sit at room-temperature for at least 15 minutes before intramuscular administration to allow the SYN023 to warm before administration. A constituted SYN023 dose if not administered immediately must be stored at temperature of 2°-8° C and administered within two hours after dose constitution. Refer to the most recent version of the Project Specific Procedures for detailed instructions regarding study drug preparation.

### **4.1.3 Disposal of Unused Supplies**

Upon completion of the study, the sponsor must provide authorization for any unused study drug and supplies to be disposed of according to the facility's SOPs. Any disposal of study drug conducted at the clinical site must be documented in the study file.

## **4.2 RIG (HyperRab ST®)**

RIG (HyperRab ST®, Grifols Therapeutics) will be supplied by inVentiv or the sponsor.

### **4.2.1 Receipt and Storage**

Upon receipt of study drug supplies, the study drug manager must immediately inspect all vials for damage. RIG will be shipped with a continuous temperature-monitoring device. Any damage or discrepancies from the packing list must be documented and promptly discussed with the sponsor and the study monitor to determine the appropriate action. RIG liquid will be stored at 2-8° C in a secured location. RIG that has been frozen should not be used. Refer to the most recent version of the Project Specific Procedures for detailed instructions regarding study drug storage.

### **4.2.2 RIG Preparation**

RIG is packaged in 2 mL and 10 mL single dose vials. After cleaning of the vial top with an alcohol swab, the proper dose of RIG is withdrawn slowly from the vial with a 21 gauge needle avoiding foaming. Study drug should be inspected for particulate matter and discarded if present. If more than one vial of RIG is required the dose may be accumulated from a second vial. RIG must be allowed to sit at room-temperature for at least 15 minutes before intramuscular administration to allow the RIG to warm before administration. A constituted RIG dose if not administered immediately must be stored at temperature of 2°-8° C and administered within two hours after dose constitution. Refer to the most recent version of the Project Specific Procedures for detailed instructions regarding study drug preparation.

### **4.2.3 Disposal of Unused Supplies**

Upon completion of the study, the sponsor must provide authorization for any unused RIG and supplies to be disposed of according to the facility's SOPs. Any disposal of study drug conducted at the clinical site must be documented in the study file.

## **4.3 RVi (Imovax®)**

RVi (Imovax®) will be supplied by inVentiv or the sponsor.

### **4.3.1 Receipt and Storage**

Upon receipt of study drug supplies, the study drug manager must immediately inspect all vials of RVi for damage. The RVi vaccine will be shipped with a continuous temperature-monitoring device. Any damage or discrepancies from the packing list must be documented and promptly discussed with the sponsor and the study monitor to determine the appropriate action. Unreconstituted RVi will be stored at 2-8° C in a secured location. Refer to the most recent version of the Project Specific Procedures for detailed instructions regarding study drug storage.

### **4.3.2 RVi Preparation**

RVi (Imovax®) is supplied in a tamper evident unit dose box with:

- One vial of freeze-dried vaccine containing a single dose
- One sterile syringe containing diluent.
- A separate plunger is provided for insertion and use
- One sterile disposable needle for reconstitution.

Cleanse the vaccine vial stopper with a suitable germicide. Do not remove the stopper or the metal seal holding it in place. Attach the plunger and reconstitution needle to the syringe and reconstitute the freeze-dried vaccine by injecting the diluent into the vaccine vial. Gently swirl the contents until completely dissolved and withdraw the total contents of the vial into the syringe. Remove the reconstitution needle and discard. Attach a sterile needle of your choice that is suitable for intramuscular injection of the subject. An RVi dose, once constituted should be allowed to sit at room-temperature for 15 minutes to allow warming and then administered. If unable to be administered immediately after room-temperature warming it should be stored at 2-8° C and should be administered within 2 hours of constitution. Refer to the most recent version of the Project Specific Procedures for detailed instructions regarding study drug preparation.

### **4.3.3 Disposal of Unused Supplies**

Upon completion of the study, the sponsor must provide authorization for any unused study drug and supplies to be disposed of according to the facility's SOPs. Any disposal of study drug conducted at the clinical site must be documented in the study file.

#### **4.4 RVa (RabAvert®)**

RVa will be supplied by inVentiv or the sponsor.

##### **4.4.1 Receipt and Storage**

Upon receipt of study drug supplies, the study drug manager must immediately inspect all vials of RVa for damage. The Rva vaccine will be shipped with a continuous temperature-monitoring device. Any damage or discrepancies from the packing list must be documented and promptly discussed with the sponsor and the study monitor to determine the appropriate action.

Unreconstituted RVa will be stored at 2-8° C in a secured location. Refer to the most recent version of the Project Specific Procedures for detailed instructions regarding study drug storage.

##### **4.4.2 RVa Preparation**

RVa (RabAvert®) is supplied in a tamper evident unit dose box with:

- One vial of freeze-dried vaccine containing a single dose
- One sterile syringe containing diluent.
- A separate plunger is provided for insertion and use
- One sterile disposable needle for reconstitution.

Cleanse the vaccine vial stopper with a suitable germicide. Do not remove the stopper or the metal seal holding it in place. Attach the plunger and reconstitution needle to the syringe and reconstitute the freeze-dried vaccine by injecting the diluent into the vaccine vial. Gently swirl the contents until completely dissolved and withdraw the total contents of the vial into the syringe. Remove the reconstitution needle and discard. Attach a sterile needle of your choice that is suitable for intramuscular injection of the subject. An RVa constituted dose should be allowed to sit at room-temperature for 15 minutes to allow warming and then administered. If unable to be administered immediately after room-temperature warming it should be stored at 2-8° C administered within 2 hours of constitution. Refer to the most recent version of the Project Specific Procedures for detailed instructions regarding study drug preparation.

##### **4.4.3 Disposal of Unused Supplies**

Upon completion of the study, the sponsor must provide authorization for any unused study drug and supplies to be disposed of according to the facility's SOPs. Any disposal of study drug conducted at the clinical site must be documented in the study file.

#### **4.5 Accountability**

The study drug manager is required to maintain accurate study drug accountability records. Instructions and forms to be completed and kept for accountability will be provided to the study drug manager. If the study drug manager wishes to use site-specific accountability forms, these must be reviewed and approved in advance by the sponsor. Upon completion of the study, all

study drug management records will be copied and the copies returned to the sponsor or its designee. The originals must be maintained at the clinical site with the rest of the study records.

## **5 SAFETY**

### **5.1 Responsibilities for Ensuring the Safety of Trial Subjects**

The national regulatory authority, the sponsor (Synermore), the institution(s) through which the research is performed and all members of the principal investigator's clinical team share responsibility for ensuring that participants in this trial are exposed to the least possible risk of adverse events that may result from participation in this protocol.

#### **5.1.1 Principal Investigator**

The principal investigator has a personal responsibility to closely monitor trial subjects and an inherent authority to take whatever measures necessary to ensure their safety. The principal investigator has the authority to terminate, suspend or require changes to a clinical trial for safety concerns and may delay an individual's study drug administration or pause study drug administration in the whole trial if the investigator has some suspicion that the study drug might place a subject at significant risk. The principal investigator determines severity and causality with respect to the study drug for each adverse event. For blinded studies the principal investigator is blinded, in which case the study drug may consist of a placebo, an active control, or the investigational product.

#### **5.1.2 Study Sponsor**

The sponsor (Synermore) also has an institutional responsibility to ensure subject safety. This responsibility is vested in a medical monitors and a safety monitoring committee.

#### **5.1.3 Medical Monitor**

The local medical monitor is the sponsor's representative and is a licensed physician or surgeon in their country of residence. The local medical monitor reviews the safety of the product for protocols in a specific region and determines expectedness of the adverse event. The local medical monitor may make a sponsor's assessment of severity and causality for adverse events that may upgrade the degree of severity and causality determined by the principal investigator. The local medical monitor, unlike the principal investigator, is unblinded for the study.

#### **5.1.4 Safety Monitoring Committee**

If study drug administration is paused (see safety pausing rules in Section 6.1) by the principal investigator, the local medical monitor, or the global medical monitor, an SMC will be convened. The SMC composition is described in an SMC charter. The voting members cannot be directly involved with the conduct of the study. Voting members cannot be employees of the sponsor. Additional subject area experts may be present to provide expertise if requested by the SMC. The SMC may review an individual SAE or it may choose to review adverse events, serious

adverse events, solicited adverse events, and laboratory and vital signs data. The SMC may unblind any amount of safety information needed to conduct their assessment. Only the SMC and the independent statistician responsible for preparing these analyses would be unblinded during these reviews. All procedures associated with this review, including objectives, data handling, and elements to be included for review will be documented in SMC minutes.

Based on its review and the protocol stopping rules (Section 6) the SMC will make recommendations in the SMC minutes to the sponsor regarding further conduct of the study and further administration of study drug. The conclusions of the SMC will be communicated to the investigators and the Institutional Review Boards/Ethics Committees and the national regulatory authority. The sponsor agrees to abide by the decision of its SMC and any directives issued by the national regulatory authority, the Institutional Review Board or Ethics Committee.

### **5.1.5 Institutional Review Boards and Ethics Committees**

The Institutional Review Board or Ethics Committee has institutional responsibility for the safety of research subjects. The Institutional Review Board or Ethics Committee has the authority to terminate, suspend or require changes to a clinical trial.

### **5.1.6 National Regulatory Authority**

Since the national regulatory authority (such as the FDA for United States) receives all expedited safety reports it also has the authority to terminate, suspend or require changes to a clinical trial.

## **5.2 Safety Surveillance During the Study**

Subjects will be monitored and safety data collected by way of clinical interviews and examinations, evaluations of daily diaries conducted by study team members, and through reports of laboratory evaluations. Time points and the specific data collected for each of these evaluations are described in Section 3 and the protocol appendices. The Medical Monitor will make the SMC aware of new safety data when it becomes available.

## **5.3 Definition of Adverse Event**

An adverse event (AE) is defined as any unfavorable or unintended sign, symptom, disease, syndrome, abnormal laboratory finding, or concurrent illness that emerges or worsens after receipt of study drug relative to the subject's pretreatment baseline, whether or not it is considered to be related to the medicinal product.

All conditions that exist prior to administration of the study drug (pre-existing conditions) will be recorded in the subject's medical history to establish baseline. Day-to-day fluctuations in pre-existing conditions that do not represent a clinically significant change in the subject's status will not necessarily be reported as adverse events.

Any adverse change from the subject's baseline condition (determined from screening evaluations conducted to confirm study eligibility) that occurs following the administration of the study drug will be considered an adverse event. This includes the occurrence of a new adverse event or the worsening of a baseline condition, whether or not considered related to the study drug. Intermittent conditions such as headaches in adults or irritability in infants may be present on Study Day 0 but may represent an adverse event if the intensity or duration of the event is worse than usual following receipt of study drug. Adverse events include but are not limited to: adverse changes from baseline that represent increases in toxicity grade according to the Toxicity Table (see protocol appendices), adverse changes in the general condition of the subject, signs and symptoms noted by the subject after study drug administration; concomitant disease with onset or increased severity after study drug administration, and changes in laboratory safety parameters occurring after study drug administration.

**The reporting period for all adverse events is specified in Table 3.1-1.** Adverse events will be reported on the Adverse Event CRF using a recognized medical term or diagnosis that accurately reflects the event. Adverse event evaluations will be reviewed by the principal investigator or by a designated medically qualified practitioner. Adverse event CRF pages are to be completed by members of the study team designated in writing by the principal investigator. The onset and resolution dates of the event and action taken in response to the event will be documented. All adverse events must be followed until resolution is demonstrated. The resolution date will be recorded on the CRF as the last date on which the subject experienced the adverse event. If an adverse event resolution date is uncertain the principal investigator should estimate the completion date based on medical judgment and interview of the subject. Approximate dates of resolution from interviews may be taken as adverse event resolution dates. Some examples of estimation of adverse event resolution are: 1) an asymptomatic laboratory abnormality on one visit that has not been followed-up between visits but has resolved by the next visit may be assumed to have resolved by the midpoint of the inter-visit interval; 2) A resolved adverse event that was treated may be assumed to have been resolved by the end of treatment. Adverse events that are still present at the end of the trial should be recorded as ongoing. Information recorded on the CRF must be substantiated in the source documents. If an adverse event evolves into a condition that becomes "serious," it will be designated as serious on the Adverse Event CRF and a supplemental SAE report form will be completed.

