**Table 3.1-1 Summary Schedule of Subject Treatment and Evaluations**

Study Visit Day →	Screen	-2	0	1	3	7	14	28	35	42	84	112
Visit Window d		0	0	0	0	1	1	3	4	4	8	11
Written informed consent	X											
Eligibility criteria verification	X											
Medical history	X											
Physical examination	X											
ECG e	X		X	X	X	X	X	X				X
Urine toxicology screen	X											
Urine βHCG (all females) e	X				X	X	X	X				X
Serum βHCG (all females) a		5										
Serum Hepatitis B, C tests	3											
Serum HIV-1,2 tests	3											
Rabies Vaccine administration			X		X	X	X	X				
Study Drug Administration			X									
Urinalysis e	X		X	X	X	X	X	X	X	X		X
Serum Anti-rabies activity e			10	10	10	10	10	10	10	10	10	10
Serum chemistry b,c	10		10	10	10	10	10	10				10
CBC, differential, platelets e	7		7	7	7	7	7	7				7
PT (INR), PTT e	5		5			5						5
Serum IgA	7											
SYN023 Pharmacokinetics e			14	7	7	7	7	7	7	7	7	
Anti-SYN023 antibodies e			5			5	5	5	5	5	5	5
Weight	X		X									X
Vital signs & oximetry	X		X	X	X	X	X	X				X
Interval history			X	X	X	X	X	X	X	X	X	X
Focused physical examination			X	X	X	X	X	X	X	X	X	X
Solicited adverse events (incl. con. meds.)			X	X	X	X	X	X				
Unsolicited adverse events (incl. con. meds.)			X	X	X	X	X	X	X	X		
Serious adverse events (incl. con. meds.)			X	X	X	X	X	X	X	X	X	X
Site of injection examination			X	X	X	X	X	X	X	X		X
Lymphadenopathy			X	X	X	X	X	X	X	X		X
Per visit phlebotomy volume	35	5	51	34	34	39	39	39	22	22	22	37
Cumulative phlebotomy volume e	35	40	91	125	159	198	237	276	298	310	332	369

- Results must be known before Study Drug administration
- Serum Chemistry: creatinine phosphokinase (CPK), troponin, total bilirubin, AST, ALT, ALP, creatinine, blood urea nitrogen, sodium, potassium, chloride, bicarbonate, calcium. Note minimum serum chemistry labs for screening visit are: AST, ALT, ALP and creatinine although other labs monitored for safety may be collected if part of panel.
- The cumulative phlebotomy volume is approximate.
- Visit window refers to acceptable variation in days either early or late from scheduled visits in without a protocol violation.
- Must be obtained on day of visit but prior to any injections.

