### **3.2.2 Screening**

A sequential site specific volunteer number will be assigned to each subject for identification purposes. Informed consent will then be obtained. Then the subject will be screened to assess eligibility for the study.

A screening log will be maintained by the site that records all subjects for whom consent was obtained and who entered the screening process. The screening log will record the sex, age and racial or ethnic identity of the candidate subjects. Abnormal results and findings resulting in ineligibility will be discussed with the subject, who will be referred for follow-up care with their healthcare provider if necessary. Only screening information from consented, eligible and dosed individuals will be entered into the study database. Eligibility for entry into the study will be based on the inclusion and exclusion criteria described below. The investigator must document confirmation of eligibility prior to randomization. The serum chemistry labs for screening visit that determine eligibility are: AST, ALT, ALP and creatinine. These are a subset of the larger clinical safety laboratory analytes. Other serum chemistry values (total bilirubin, BUN etc.) that are collected for safety monitoring (Table 3.1-1) will be collected for Study Day 0 baseline values but are not part of the inclusion/exclusion criteria as such.

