### **3.6.3.5 Clinical Assessments and Laboratory Tests**

#### **Abnormal Clinical Assessments and Laboratory Tests**

Results from clinical laboratory tests obtained on the study must be reviewed by the investigator (or a designee who is a medically qualified study team member) within 72 hours of receiving the results to determine if abnormalities exist. If the laboratory value is abnormal and has increased in toxicity grade (see Appendix E for toxicity grading scales) from baseline values, it must be reported as an adverse event and repeated promptly to demonstrate resolution. Additional laboratory tests may be performed if the investigator deems them to be necessary to fully evaluate an adverse event. In the event that the investigator elects to order non-protocol-specified laboratory tests, the investigator must record the rationale for the tests and a determination of clinical significance of the result in the source documents. The investigator must keep the medical monitor informed of adverse events of clinical significance.

Abnormal results and findings will be discussed with the subject, or the subject will be referred for follow-up with their healthcare provider if necessary.

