### **5.13 Adverse Event Treatment, Follow-up, and Outcome**

Treatment of any adverse events will be determined by the investigator using his/her best medical judgment and according to current clinical practice guidelines. All treatments as well as follow-up will be recorded in the appropriate CRF.

Adverse events will be considered resolved when the condition returns to normal or returns to the subject's baseline status as established on Study Day 0, or when the condition has stabilized with the expectation that it will remain chronic.

The investigator will continue follow-up on adverse events, including laboratory abnormalities and solicited adverse events, until the event has resolved, is otherwise satisfactorily explained, or the subject completes the study.

Follow-up for serious adverse events must continue until resolution and the outcome reported to the sponsor, even if this extends beyond the serious adverse event reporting period (i.e., after the final study visit). For analysis purposes, the outcome for serious adverse events will be determined on the final study visit.

Outcome of all adverse events will be classified as one of the following:

- Resolved
- Resolved with sequelae
- Ongoing
- Death

If at any time after completion of the serious adverse event reporting period (the final study visit) the investigator becomes aware of a serious adverse event that is suspected by the investigator to be related to the study drug, the event must be reported to the sponsor.

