9.3 Laboratory Parameters

Clinical laboratory (serum chemistry, hematology, and urinalysis) testing will be performed at screening, on Day 0, Day 1, Day 3, Day 7, Day 14, Day 28 and Day 112. In addition Urinalysis will be performed on Day 35 and Day 42. Coagulation tests will be performed at screening, Day 0, Day 7 and Day 112.

Serum chemistry parameters should include the following: creatinine phosphokinase (CPK), troponin, total bilirubin, Aspartate aminotransferase (AST), Alanine aminotransferase (ALT), Alkaline phosphatase (ALP), creatinine, blood urea nitrogen, sodium, potassium, chloride, bicarbonate, calcium.

Hematology parameters should include the following: complete blood count with differential, hemoglobin, hematocrit, and platelet.

Coagulation parameters should include the following: Prothrombin time (international normalized ratio) (PT (INR)) and Partial thromboplastin time (PTT).

Urinalysis parameters should include the following: macroscopic examination, pH, specific gravity, protein, glucose, ketones, bilirubin, occult blood, nitrite, urobilinogen, and leukocytes. Unless otherwise specified, microscopic examination will be performed on abnormal findings only and results will be listed.

Listings of all clinical test results (serum chemistry, coagulation, hematology, and urinalysis) will be provided with the abnormal values flagged with “L” for low and “H” for high for continuous parameters, and “A” for abnormal categorical parameters.

Descriptive statistics (mean, median, SD, Min, Max, and sample size) will be presented overall for screening and by the associated current treatment for on-study measurements for each clinical laboratory test (continuous variables). Change from baseline descriptive statistics for on-study measurements will also be presented. Baseline will be defined as the last results (scheduled or unscheduled) obtained prior to the first study vaccine administration. For categorical variables (urinalysis tests), the number of subjects (frequency and percentage) will be tabulated for each individual result (e.g. negative, positive, trace). Results from repeat tests will not be included in the summary statistics unless the repeat was required (and documented as such) due to technical reasons or an invalid initial result.

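### Protocol 5.3 ties the adverse-event baseline to screening, while 5.13 and the rest of the plan use Study Day 0 or the last pre-dose value (minor)

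*Protocol*

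**What the plan says.** **Onset.** Protocol 5.3 opens with a general definition: an event that "emerges or worsens after receipt of study drug relative to the subject's pretreatment baseline". No day is given. A later paragraph of the same section is specific and refers to the "baseline condition (determined from screening evaluations conducted to confirm study eligibility"). It limits the rule to changes that occur after Study Drug.

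**Mandatory laboratory events.** Section 3.6.3.5 says that an abnormal value that "has increased in toxicity grade (see Appendix E for toxicity grading scales) from baseline values, it must be reported as an adverse event". It does not say which visit supplies the baseline values.

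**Resolution.** Section 5.13 treats an event as resolved when, among other possibilities, the condition "returns to the subject's baseline status as established on Study Day 0".

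**Laboratory baseline elsewhere.**
- Section 3.2.2 says that chemistry values not needed for eligibility "will be collected for Study Day 0 baseline values".
- Section 3.2.5 lets specimens from Day -2 onward stand as baseline without a redraw.
- Appendix A calls Day 0 the baseline visit.
- Section 7.6.2 summarises change from before to after Study Drug.
- SAP 9.3 states: "Baseline will be defined as the last results (scheduled or unscheduled) obtained prior to the first study vaccine administration". SAP 9.4 and 9.5 use the same rule for vital signs and ECG.

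**What is drawn at screening.** The notes to Table 3.1-1 say: "Note minimum serum chemistry labs for screening visit are: AST, ALT, ALP and creatinine". Appendix A requires the full panel on Day 0.

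**The concern.** The paragraph in 5.3 is the only place that ties adverse-event onset to a particular visit, and it names a different visit from the one used for resolution and for laboratory change. Because 3.6.3.5 leaves the day open, a site that looks to 5.3 for the meaning of baseline will grade laboratory changes against screening. A site that looks to 3.2.5, 5.13 or Appendix A will grade them against Day 0. The same series of results can then be reported as an adverse event or left out.

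This matters because 7.6.1 makes the number and percentage of adverse events the primary variable for the safety profile and brings laboratory abnormalities into the adverse-event summary. Comparing safety with RIG or SYN023 is a secondary objective.

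**Working it through.** The plan states no figure here to reproduce. The check is a reading of the rules, a count of analytes and two graded examples.

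**1. Possible gap between the two baselines.** Section 3.2.5 allows screening up to 28 days before Day 0. Where the specimen is drawn on Day -2 or later and not redrawn, the two baselines are the same value.

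**2. Analytes with no required screening value.**
- Full panel (Table 3.1-1 notes; same list for Day 0 in Appendix A): CPK, troponin, total bilirubin, AST, ALT, ALP, creatinine, BUN, sodium, potassium, chloride, bicarbonate, calcium = 13.
- Required at screening (Table 3.1-1 notes, 3.2.2, Appendix A): AST, ALT, ALP, creatinine = 4.
- Not required at screening: 13 - 4 = 9, and 9/13 = 69%.
- Exclusion 3 also names total bilirubin at screening. If that makes it a required test, 13 - 5 = 8, and 8/13 = 62%.
- Required on Day 0 before Study Drug: 13 of 13.

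**3. Value raised at screening, normal on Day 0, raised after dosing.** Exclusion 3, as worded, lets a single AST, ALT or ALP exceed the upper limit of normal (ULN) by more than 10%. Appendix E grades ALT of 1.1 to 2.5 x ULN as Grade 1. Illustrative ALT values:

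| | Screening | Day 0 | Day 7 |
|---|---|---|---|
| ALT (x ULN) | 1.2 | 1.0 | 1.2 |
| Grade | 1 | 0 | 1 |

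- Change from screening: 1 - 1 = 0, so 3.6.3.5 is not triggered.
- Change from Day 0: 1 - 0 = 1, so 3.6.3.5 requires an adverse event.

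**4. The reverse pattern.**

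| | Screening | Day 0 | Day 7 |
|---|---|---|---|
| ALT (x ULN) | 1.0 | 1.2 | 1.2 |
| Grade | 0 | 1 | 1 |

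- Change from screening: 1 - 0 = 1.
- Change from Day 0: 1 - 1 = 0. The value also equals the Day 0 status that 5.13 accepts as resolved.

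On grade alone the two baselines disagree in both directions. How far the rest of 5.3 settles each pattern is taken up next.

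**The case against.** The strongest reply is that 5.3, read in full, settles most of this, and much of that reply stands.

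- **Pre-dose changes charged to study drug.** A reader might infer this from the reverse pattern. The 5.3 sentence covers only changes that occur after Study Drug. In step 4 the change came before dosing and nothing worsened afterwards, so 5.3's own words largely exclude it.
- **True post-dose rises definitely lost.** A reader might infer this from step 3. The opening definition in 5.3 uses the state before treatment, and its list of examples is open-ended and includes laboratory changes after Study Drug. Both point towards counting the Day 7 value. What remains is that the sentence naming a visit names screening, and that 3.6.3.5 does not override it. Two readings are open and one leaves the event out.
- **Nine analytes without a baseline.** They lack only a required screening value. Each has a required Day 0 value, so no baseline data are missing.
- **Adverse-event tables contradicting the SAP shift tables.** SAP 9.3 shift tables use low, normal and high against reference ranges, not toxicity grades, so the two need not match under any baseline. The SAP's change-from-baseline summaries are unaffected.
- **Bias between RIG and SYN023.** Arms are randomised, follow the same visit schedule and are assessed by a blinded principal investigator (3.4). SAP section 9 plans no inferential safety analysis. Nothing in the documents gives the ambiguity a direction.

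**Conclusion.** The inconsistency is in the text. Section 5.3 names screening for onset, 5.13 names Day 0 for resolution, and the laboratory provisions and SAP follow Day 0 or the last pre-dose value. The wording in 5.3 is the outlier. The consequence that survives is the step 3 pattern, where a mandatory laboratory adverse event could be left out depending on which sentence the site follows. That example relies on exclusion 3 as worded.

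The effect is on adverse-event classification only. It is probably small, and the documents give no figure for it. A reader might try to size it by assuming that 2% to 5% of subject-analyte pairs change grade between screening and Day 0: 160 x 4 = 640 pairs, 640 x 0.02 = 13 (rounded) and 640 x 0.05 = 32. The documents do not support that rate. The result would also count pairs with two candidate baselines, not misclassified events, which need a particular post-dose pattern as well. It should not be quoted as the size of the problem.

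Severity: minor. Confidence is high in the wording conflict and low in any numerical impact.

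**What to change.** 1. In Protocol 5.3, replace the words in parentheses with: the last assessment before Study Drug on Study Day 0, including specimens taken on or after Study Day -2.
2. Cross-reference this single baseline in 3.6.3.5 (grade increase) and 5.13 (resolution).
3. In SAP 9.3, 9.4 and 9.5, change the anchor from the first study vaccine to Study Drug. Under Protocol 3.5 the vaccine follows Study Drug by up to 75 minutes, and 3.6.3.1 has vital signs taken between the two, so the present wording could admit a reading taken after Study Drug as baseline.
4. In the same edit, reconcile 3.2.2 with exclusion 3 on whether total bilirubin is a screening test.

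The cost is one phrase in 5.3, two cross-references, one phrase repeated in three SAP sections, the bilirubin reconciliation and a matching line in the CRF guidelines. The baseline change itself needs no new data, because the Day 0 values are already collected. Protocol section 12 requires IRB/IEC approval of protocol changes, so this can go with the next amendment.
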